## **Risks to Subjects**

### **a. Human Subjects Involvement and Characteristics**

Participants will be 192 Veterans ≤ 55 years of age receiving clinical care at the VAPSHCS and VAPORHCS

(Portland and Vancouver campuses) and affiliated clinics, who meet diagnostic criteria for comorbid mTBI/PTSD. Employees or students, pregnant women, economically and/or educationally disadvantaged persons, and terminally ill patients will be included. Based on the nature of the intervention, it is anticipated that this treatment will present minimal risk to these populations. Individuals with impaired decision making capacity, illiterate, or who have limited or no English language proficiency will be excluded on the basis of possible diminished cognitive ability that would compromise their involvement in this treatment. Prisoners will be excluded from the study as a result of this study being conducted on an outpatient basis only. There will be no restrictions on, ethnicity, or race, and both men and women will be included. Recruitment fliers will specifically include the statement, "women and members of minority groups are encouraged to participate." Additional inclusion criteria include: 1) Diagnosis of PTSD made by use of the Clinician Administered PTSD Scale (Blake et al., 1990); 2) screened positive for mTBI on the Structured Interview for Collecting Head Trauma Event Characteristics as outlined by the VA/DoD Clinical Practice Guideline for Management of Concussion/mTBI and positively endorsed any of the Neurobehavioral Symptom Inventory (NSI; Cicerone & Kalmar, 1995) cognitive symptoms items (items 13-17); 3) English speaking, willing to attend weekly treatment telehealth sessions (if randomized to the CABA condition) and the follow-up assessments, and willing to refrain from additional treatment for PTSD during the first 3 1/2 months of the active phase of treatment if they are assigned to the CABA condition; and 4) willingness to participate in audio-recorded sessions.

## **b. Sources of Materials**

Several sources of information will serve as data for the study, including neuropsychological assessments and standardized diagnostic interviews and questionnaires administered by study personnel, audiotaped treatment sessions for individuals assigned to the CABA group (to be used for supervision, determination of adherence and competence in the intervention, achieving reliability in ratings of adherence and competence and training purposes), daily monitoring forms for individuals in the CABA group, and information from medical records. Other than the information derived from the medical records, data will be collected solely for research purposes. However, because of the clinically-relevant nature of much of this information, patients will be informed that these data may be reported in their medical record, as clinically indicated. Data will be labeled with a code number that is unique to each patient in the study. All hard copy data will be stored in locked filing cabinets in locked rooms, while all electronic data will be stored in password-protected files in a limited access folder on the secure VA network drive. Data may be temporarily stored in a locked filing cabinet at the American Lake division until it can be transported to the Seattle VA. Data will be transported between American Lake and Seattle divisions by study staff in HIPAA-compliant locked containers. Each study site will maintain a key code that links that site's patients with their coded identifier. This key code will be stored separately from all other study data and available and maintained only to the multisite co-PIs, the site PI's, the multi-site project coordinator, and the site coordinators and research assistants. Any materials with protected health information (e.g., Informed Consents) will be stored in separate locked filing cabinets from coded materials to ensure the security of patient privacy.

## **c. Potential Risks**

Minimal risk is anticipated with the current investigation. The psychotherapeutic intervention under investigation is consistent with the treatments recommended in the VA/DoD Clinical Care Guidelines for the treatment of PTSD and mTBI. Participants randomized to TAU will have identical opportunities for treatment as non-research patients. Regarding research risk, participants may experience anxiety and/or distress during the assessment procedure and during the course of treatment. Participants may also experience discomfort as a result of being audio recorded during the course of therapy. Participants also might not experience symptomatic relief from the intervention. Potential study participants will be informed that they may choose not to participate in the study without risk to their medical care, and that similar interventions not being evaluated in the study are available in the facility without participation in the research.

All study personnel who conduct the assessments and interventions will be qualified, trained, and closely supervised by the co-Principal Investigators (co-PIs). Participants will be provided with emergency contact numbers. All participants will be clearly informed of their right to withdraw from the study at any point without adversely impacting their routine medical, psychiatric, or psychotherapeutic care.

Safety monitoring will be performed by the study staff who conduct interviews, administer assessment questionnaires, conduct psychological and cognitive assessments, and conduct interventions. Adverse events will be reported immediately to the co-PIs, who will examine the patient and determine if any additional evaluation or treatment is needed. The co-PIs will recommend termination of participation, provide appropriate referrals, and engage in follow-up if substantial decline in functioning is observed. Referral will also be offered to non-responders and any participant who requests further treatment. The co-PIs will ensure that adverse events are properly reported to the IRB. The co-PIs will review all cumulative adverse events quarterly to determine if there are any systematic problems as the co-PIs will be ultimately responsible for all safety monitoring conducted for this study.

Although the proposed study poses no serious risks to participants, participants may notify research personnel about pre-existing mental health issues that have not been previously identified by other VA providers. Therefore, participants will be referred to the VA's Mental Health Division for further assessment and/or treatment if a previously undiagnosed psychiatric disorder is identified. We will inform participants of this procedure as part of the informed consent process and participants must agree to this procedure to be eligible to participate in the study. This ensures that we can adequately manage any pre-existing clinical issues that become apparent through subject evaluation.

## **Adequacy of Protection from Risks**

### **a. Protection Against Risk**

Trained, closely supervised staff will conduct the assessments and the intervention. Assessors conducting diagnostic psychiatric interviews will have at least one year of graduate experience or equivalent work experience, and therapists will be master's or doctoral level. Drs. [name] and [name], licensed clinical psychologists, will review weekly therapy tapes and attend to any difficulties encountered. In addition, participants will be provided with emergency contact numbers. Finally, all participants will be clearly informed of their right to withdraw at any point and Drs. [name] and [name] will recommend termination of participation (and provide appropriate referral and follow-up) if substantial decline in functioning is observed (including significant increase in alcohol or drug use). Referral will also be offered to nonresponders and any participant who requests further treatment. Specific procedures will be maintained to maximize the likelihood that participant research related material will be secure and confidential. Data will be stored in locked filing cabinets and computer databases, without names or other potentially identifiable information attached; identifiable information will be kept separately and a coding system will be used to link data and identifiers.

All SAE's, UAP's, and protocol deviations occurring at either site will be communicated to the Co-PI's immediately and necessary documentation will be submitted to the CIRB within stipulated timeframes and via designated channels in accordance with the VA Central IRB Table of Reporting Requirements.

All study personnel will follow the policies and procedures for suicide prevention and management of suicidal behavior and its aftermath anywhere within the medical center or on the premises as outlined in the VAPORHCS Medical Center Memorandum No. 11-04 and in Memorandum TX-74 for Seattle both included in the study Suicide behavior protocol, Appendix A.

**Imminent risk Protection:** The following protocol applies to participants who express indication of imminent risk or clinical emergency; this includes concerns about suicidality and homicidality.

Participants may express indicators of risk either to the study clinician or to the study assessor; the protocol differs for each of these groups and is discussed below:

**For study clinicians:** If a participant presents to his/her study clinician/Interventionist with a clinical emergency (e.g. suicidality), the study clinician should address the situation as clinically appropriate. Concerns about imminent risk should be prompted by an examination of the participant's response to item #9 on the BDI (score > 2) and/or clinical inquiry. The clinician must assess and intervene within the study treatment protocol but is not limited by the parameters of the protocol in cases of imminent risk. Instead, in such cases, clinicians should address these situations consistent with optimal standards of care including hospitalization if required (see Suicidal/Homicidal Behavior Protocol in Attachment A).

In addition, any concerns of imminent risk among participants in the CABA condition are to be immediately communicated to the site investigators ([name]. at the VAPORHCS and [name]., at the VAPSHCS), including the course of action taken. The site PIs will review such cases and determine if additional intervention is necessary. This review and/or evaluation is not required of participants in the control group as they will be receiving usual VA care and evaluation and intervention for imminent risk will follow standard VA procedures.

**For study assessors:** Study assessors should follow the Suicidal/Homicidal Behavior Protocol under the following conditions: if a participant presents with a score of 2 or higher on item 9 on the Beck Depression Inventory, or when there is other information that suggests that the person may be at risk. Assessors must also contact the site investigators who will determine if additional intervention is necessary; this review and/or evaluation is not required of participants in the control group as they will be receiving usual VA care and evaluation and intervention for imminent risk will follow standard VA procedures. Participants may be connected via a "warm transfer" with the National Veterans Crisis Line or be instructed to go to their nearest medical facility's emergency department.

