**Clinical** providers may refer interested patients and document their willingness to be contacted by the study through CPRS via their progress notes and using templated language provided to them (See Appendix G). Clinicians may also send referral information via encrypted email with the same templated documentation (or comparable documentation that the Veteran is interested in hearing more about the study and gives permission for research staff to contact them). Following a chart review and preliminary phone screen to determine eligibility, potential participants will be scheduled for an initial telehealth (by video or telephone) appointment during which they will be consented to the study. Consented participants will be instructed to return the informed consent form (ICF) and Authorization for Use and Release of Individually Identifiable Health Information Collected for VHA Research (HIPAA form) to the study team using a prepaid and preaddressed envelope. Once received, a study team member will complete an assessment appointment with the participant via telehealth. After all eligibility criteria are met and the assessment is complete, if telehealth appointments are conducted via VA Video Connect (VVC) platform, participants may receive automated reminders and appointment links over email, consistent with procedures for clinical appointments using VVC. The study statistician will randomly assign eligible participants to one of the two treatment options and will notify the site study coordinator about randomization status. The site study coordinator or other appropriate research team member, will contact the participants to inform them of their group assignment. Those assigned to CABA will be contacted by their therapist and tele-or video-therapy will commence. Those assigned to TAU will be offered a referral for PTSD specialty care. The assessors will be blind to group status throughout the study whenever possible. Consistent with a national VA performance measure that requires 8 sessions to be delivered over a 14 week period, participants will be contacted by phone by a blinded assessor for the mid-treatment assessment 7 weeks after the onset of treatment. Allowing 14 weeks to complete a 10 session treatment protocol accounts for cancellations and missed sessions. Participants will then be seen for follow-up assessments 14 weeks after initiating treatment. In order to minimize drop-out and maximize retention of individuals for intent-to-treat analyses, extensive efforts will be made to stay in contact with all study participants, including individuals who drop out of treatment. CABA participants who are deemed nonresponders or relapsers (do not evidence at least a 20% reduction in PTSD or cognitive symptoms) at the post-assessment or follow-up assessment (or an increase in suicidality or substance abuse), and other participants as clinically appropriate, will be offered alternative treatment or appropriate referrals.

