
**Blinding:** Subject and facilitator blinding is not feasible due to the study design: a treatment group vs. a usual care group. The assessors will be blind to group status throughout the study.

**Randomization:** Randomization tables will be prepared by [name], the statistician, at the beginning of the study, and he will notify the site study coordinator of the participant's randomization status. Over the course of the study, [name] will monitor enrollment; if imbalance occurs, he will recommend appropriate adjustment.

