**DATA SAFETY MONITORING:** Safety monitoring analyses will occur every six months from study inception through completion. The unblinded data manager will provide the blinded study statistician with a limited data set containing blinded group membership data, i.e., group membership that is numerically labeled but unidentifiable as treatment vs. control group. This dataset will also contain in-progress data safety variables including CAPS scores and any serious adverse events including 1) the onset of imminent risk of harm to self or others such as active thoughts of suicide or violence with expressed plan and intent to act; 2) the onset of psychotic and or manic symptoms; 3) a decline in global daily functioning indicating that inpatient mental health services are required for stabilization; 4) the onset or exacerbation of major medical illness that interferes with participation in regular outpatient mental health services. Differences between the treatment and control groups will be analyzed using t-test comparisons. We will consult with the CIRB and consider the appropriateness of study suspension if, at the set data monitoring time periods every six months, we find that either group of participants is experiencing, on average, an increase in CAPS scores of 12 or more points and/or is experiencing, on average significantly more SAE's including those defined above. For serious adverse events, significance is defined as a statistically significant difference of  $p < .01$  and/or a large effect size equivalent to a Cohen's  $d$  value of .8 or greater. The two study PIs will be responsible for notifying and consulting the CIRB of any conditions meeting criteria for possible study suspension within one business day of discovery.

Randomization procedures as well as overall multisite study interim, data safety monitoring and final data analyses will be conducted by our contracted statistician, [name] who is affiliated with University of California, San Diego. [name] will receive a limited data set copied in encrypted format onto CD's sent via secure FedEx with tracking services. This data set will be considered a limited data set due to inclusion of patient assessment dates and otherwise is de-identified. A Data Use Agreement will be pursued between the VAPORHCS and [name] recognizing the agreement of the terms for use of this data which shall be transmitted and accessed strictly for data analysis purposes pursuant to the goals of this study.

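### The imminent-risk instruction contains a control-group exemption that an assessor cannot use while blind, and the plan does not say how TAU imminent-risk events reach the between-arm SAE comparison, so ascertainment may be unequal.

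*Combined protocol and SAP*

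**What the plan says.** **Assessors (a. Protection Against Risk).** The trigger is the same in both arms: the Suicidal/Homicidal Behavior Protocol applies "if a participant presents with a score of 2 or higher on item 9 on the Beck Depression Inventory", or when other information suggests risk. The duty to notify follows: "Assessors must also contact the site investigators who will determine if additional intervention is necessary". The same sentence ends with the control-group exemption, worded as in the paragraph for clinicians: "This review and/or evaluation is not required of participants in the control group". The reason given is that these participants receive usual VA care.

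**Study clinicians (same section).** Escalation is written for one arm: "any concerns of imminent risk among participants in the CABA condition are to be immediately communicated to the site investigators". The clinicians' item 9 prompt is a score above 2, whereas the assessors' is 2 or higher.

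**Blinding.** The Blinding paragraph of section 5.1 is unqualified: "The assessors will be blind to group status throughout the study". The Procedures paragraph of the same section softens it: "The assessors will be blind to group status throughout the study whenever possible".

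**Safety comparison (5.6 Data Analysis, Data Safety Monitoring).** The first SAE listed is "the onset of imminent risk of harm to self or others". Groups are compared by t-test every six months. A difference at p < .01 and/or a Cohen's d of .8 or more leads to consultation with the CIRB about suspension.

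**Who watches for events.** c. Potential Risks says: "Safety monitoring will be performed by the study staff who conduct interviews". The sentence goes on to staff who carry out assessments and interventions. Section 5.7 counts treatment visits as occasions for observing decline in CABA only.

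**The concern.** There are two separate problems.

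The first is blinding. Participants and therapists know the arm, so assessor blinding is the main protection for CAPS-V, a Hypothesis 1a outcome. The instruction offers assessors an exemption that depends on arm and does not say that someone else applies it. An assessor who tries to use it must find out the allocation.

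The second is ascertainment. Imminent risk is a listed SAE, and the SAE rates of the two arms are formally compared. In CABA, a study therapist sees the participant through ten sessions and must escalate concerns. In TAU, treatment is given by usual-care clinicians, who have no stated reporting line to the study. If fewer TAU events reach the dataset, an apparent CABA excess may be an artefact. A true TAU excess may also be hidden, so a null result would not be reassuring either.

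**Working it through.** **1. Can the exemption be used blind?** Taking the assessor sentence in parts:
- The trigger (item 9 or other risk information) does not depend on arm.
- The notification of site investigators is mandatory and carries no arm condition of its own.
- The exemption makes the review and/or evaluation not required in the control group, so it depends on arm.

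A blinded assessor can carry out the first two parts for everyone. Only the third needs the allocation, and the text names nobody to apply it.

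**2. How far could unblinding reach the primary outcome?** Table 3 schedules CAPS-V at weeks 0 and 14, and BDI-II at weeks 0, 7 and 14. Week 0 precedes randomization. Exposure is therefore a week 7 trigger carried forward to week 14 (if the same assessor rates both), or a week 14 trigger if BDI-II is scored before CAPS-V in that visit. The documents settle neither point.

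**3. Scheduled study-staff contacts after randomization (Table 3).**
- CABA: visits 2–6 (5) + visit 7 (1) + visits 8–12 (5) + visit 13 (1) = 12.
- TAU: visit 7 (1) + visit 13 (1) = 2.

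TAU participants are also offered PTSD specialty sessions, but not with study staff.

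**4. What would unequal capture do to the SAE flag?** The plan states no event rate or capture rate, so there is no figure to reproduce. The following is an illustration under assumptions:
- n = 96 per arm (section 5.2).
- True risk p is the same in both arms: 5%, 10% or 20% (assumed).
- Capture is 100% in CABA and c in TAU (assumed).
- The SAE is coded 0/1 per participant and there is a single look (assumed; the plan does not specify the coding).

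With m₁ and m₂ the recorded proportions, v = n[m₁(1−m₁) + m₂(1−m₂)]/(2n−2), t = (m₁−m₂)/√(2v/n) and d = (m₁−m₂)/√v. A flag is p < .01 on 2n−2 = 190 df.

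Worked example at the expected proportions, p = 20% and c = 50%, so m₁ = .20 and m₂ = .10:
- v = 96 × (.16 + .09)/190 = .1263, so √v = .355.
- d = .10/.355 = .28, and t = .28 × √48 = 1.95.
- The two-sided 1% critical value on 190 df is about 2.60. The expected t is below it, but sampling variation carries t past it in roughly a quarter of trials.

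Simulated chance of a false p < .01 flag (40,000 runs per setting, no true difference, 96 per arm):

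| TAU capture | risk 5% | risk 10% | risk 20% |
|---|---|---|---|
| 100% | 0.9% | 1.0% | 1.1% |
| 75% | 1.2% | 2.5% | 4.7% |
| 50% | 3.2% | 10.3% | 26.0% |
| 25% | 8.2% | 35.1% | 74.7% |

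At 48 per arm and 50% capture, the figures are 0.3%, 2.9% and 10.0%. The d ≥ .8 criterion is almost never met at 96 per arm (at most 0.5% in any setting).

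**The case against.** A reader might infer that a blinded assessor cannot follow the rule at all. The text does not support that. An assessor who notifies the site investigators about every triggered participant complies and stays blind, and site staff who know the arm could then apply the exemption. This part of the objection stands. What remains is that the text does not instruct it, and it places the exemption inside the assessor's own instruction.

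A reader might also infer that the plan does capture more events in CABA. The exemption covers review, not SAE recording. c. Potential Risks, a. Protection Against Risk and section 6.0 send AEs and SAEs from both arms to the co-PIs without excepting TAU. The plan also uses medical records as data, records all treatment received and asks about treatment changes at follow-up. This too stands, so unequal capture is a possibility and not a finding. These duties govern events that study staff know about, however. None says how an event handled only under standard VA procedures comes to their notice or enters the safety dataset. The suicide behavior protocol in the appendix may say, but it is not among the documents.

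A numerical example can mislead here. With 5% true risk and assumed capture of 90% v 50%, the arms would record 96 × .05 × .9 = 4.3 and 96 × .05 × .5 = 2.4 events, a ratio of 1.8. Those capture rates have no source in the documents. Proportions of 4.5% v 2.5% give d of about 0.11 and t of about 0.75, well short of either criterion.

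Nor is this the only safety check: the same section monitors CAPS change with a 12-point criterion, measured on the same schedule in both arms. Meeting a criterion prompts consultation, not automatic suspension.

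**Conclusion.** The point holds in limited form. The control-group exemption in the assessor instruction conflicts with the unqualified blinding statement, and the plan does not say who applies it. The threat to CAPS-V is confined to participants who trigger the rule at week 7 or 14.

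Separately, scheduled study contact after randomization is 12 v 2 and mandatory escalation by therapists exists only in CABA. No stated route brings TAU events handled in usual care into the SAE comparison, which may therefore be subject to unequal ascertainment. Its size cannot be derived from the documents. Under equal true risk of 5% to 20%, full CABA capture, 96 per arm and one look, the false p < .01 rate is 0.9% to 1.1% with equal capture, 1.2% to 4.7% at 75% TAU capture and 3.2% to 26.0% at 50%. The effect is small if TAU capture is nearly complete or events are rare, and material otherwise.

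The two item 9 thresholds are a further inconsistency: a score of exactly 2 meets the assessors' trigger but not the clinicians' prompt.

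**What to change.** - Reconcile the Procedures and Blinding paragraphs of section 5.1, the assessor instruction in a. Protection Against Risk, and Data Safety Monitoring in section 5.6, so that a blinded assessor's notification step does not require knowledge of arm. Any exemption should be applied by staff who already know the allocation. Whether control-group participants receive investigator review is a clinical matter for the sponsor.
- State how a TAU imminent-risk event handled under standard VA procedures enters the safety dataset.
- Add a field to the SAE form for the source of each event (scheduled assessment, study therapist, medical record, other).
- At each six-monthly review, show the between-arm SAE comparison twice: for all events, and for events from sources common to both arms (scheduled assessments, and the medical-record and treatment data already collected). Therapist-reported CABA events stay in the overall safety review, because removing them would reduce sensitivity to harm from the experimental treatment.
- Reconcile the two item 9 thresholds.

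The cost is protocol wording, one form field, one extra tabulation and a few more notifications to site investigators. If medical records are not already read for SAEs during follow-up, some abstraction time is added. The common-source table will hold fewer events, so it should be read beside the full one and not in its place.
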